7.11 Correlative Studies

7.11.1 Correlative Blood Samples

Research blood samples (50cc) will be drawn at baseline, on cycle 1 day 8, cycle 1 day 15, on day 1 of each subsequent cycle, and at the end of study visit. Immune markers such as multi-parameter flow cytometry, antigen-specific T-cell assays (to identify tumor-reactive T-cells), markers of APC activation, T-cell receptor sequencing, and/or cytokine assays will be performed. Depending on resource and sample availability, additional assays to further assess immune activation following treatment will be employed.

Further procedures for handling of research blood samples are described in the laboratory manual.

7.11.2 Tumor Biopsy

Tumor tissue samples will be obtained at baseline and between days 15 and 19 of cycle 1. Biopsies are mandatory but can be omitted if in the best interest of the subject after discussion with the Principal Investigator. At a minimum, tissue confirmation of histology (HCC) and RB status by immunohistochemistry is required prior to starting study therapy. Tissue will be analyzed by H&E, and by IHC for PD-L1 and for

CONFIDENTIAL

immune markers (such as CD45, CD68, CD3, CD8, CD4, Foxp3, CD20, myeloperoxidase), tumor markers (AFP, Ki-67, cleaved caspase 3), vascular (CD31) and stromal markers (collagen type I); and by Masson's trichrome. If sufficient material is available, the tumor may also be assessed by a next-generation sequencing panel, whole exome sequencing (WES), RNA sequencing, and/or by other techniques. When tumor WES sequencing, tumor RNAseq, and germline WES is feasible and successfully performed, patient specific neo epitopes arising from tumor somatic missense mutations will be predicted bioinformatically.

Depending on resource availability and tissue availability, additional assays to further assess immune activation following treatment will be employed. In some cases, germline whole exome sequencing will be performed to allow determination of HLA type and as needed for the bioinformatics pipeline to identify patient specific neo epitopes.

Further procedures for handling of tumor biopsy material is described in the laboratory manual.

8 Statistical Plan

8.1 Primary Endpoint

The primary endpoint is overall response rate (ORR) by investigator review using RECIST v. 1.1 (binary).

8.2 Secondary Endpoints

1. Toxicity rates is an ordinal measure, graded using CTCAE v. 5.0, or dichotomized (binary).
2. Overall response rate using iRECIST criteria (binary)
3. Progression-free survival (time to event)
4. Duration of response (time to event)
5. Overall survival (time to event)

8.3 Sample Size and Power Determination

Overall response rate to PD-1 therapy in HCC has varied in published studies from 15-20%. By combining available data from these studies, an overall response rate of 18% is estimated for PD-1 monotherapy. Doubling of this response rate, from 18% (H0) to at least 36% (H1) would be highly promising and worthy of additional study. With 27 subjects, a one-sided binomial test with alpha = 0.10 will have 81% power to detect an improvement in ORR from 18% (H0) to 36% (H1). For proportions, a sample of n=27 will provide 90% confidence intervals that are a maximum of 0.34 in width. For additional time to event variables, 27 subjects (21 events by 24 months) yields 90% confidence intervals for median survival that are approximately half of mean survival in width (assuming exponential survival).

8.4 Statistical Methods

ORR and other binary variables will be analyzed using binomial exact tests, using a one-sided 10% type one error. Progression-free survival, duration of survival, and overall survival will be analyzed using Kaplan-Meier methods. PFS and DOR will be summarized as medians with 90% confidence intervals. Toxicity rates will be summarized as binomial proportions with 90% confidence intervals.

8.4.1 Baseline Data

Baseline and demographic characteristics will be summarized by standard descriptive statistics (including mean and standard deviation for continuous variables such as age and standard percentages for categorical variables such as gender).

8.4.2 Efficacy Analysis

To be eligible for efficacy endpoints (PFS, ORR, DOR, OS), subjects must have completed at least one cycle of therapy, and have had their disease re-evaluated by appropriate cross-sectional imaging (CT or MRI) at least 4 weeks and no more than 12 weeks after their baseline imaging. Subjects who do not meet criteria for the efficacy analysis will be replaced.

CONFIDENTIAL

This material is the property of the University of Pennsylvania.

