1.3.1 Nivolumab In Hepatocellular Carcinoma

Nivolumab was initially tested in hepatocellular carcinoma in the phase I/II Checkmate-040 study [3]. This was an open-label, non-comparative dose escalation and expansion trial. A total of 262 subjects were treated in the two phases of the study. In the dose-escalation portion, the overall response rate was 15%, with a disease control rate of 58% and a median overall survival of 15.0 months. In the dose expansion phase, an objective response rate of 20% was demonstrated, and median survival was not reached in the overall population. Response rates were similar regardless of viral hepatitis status or prior treatment with sorafenib. Toxicity was manageable, with 25% grade 3/4 adverse events, most commonly rash (23%), AST increase (21%), ALT increase (15%), lipase increase (21%), amylase increase (19%), and pruritis (19%). Treatment-related serious adverse events were seen in 6% of patients in the dose-escalation of cohort. Only 20% of subjects had PD-L1 expression of > 1% by IHC, and this did not correlate with response rate. Based on the results of this study, nivolumab received accelerated approval from the FDA for HCC. A phase III trial (Checkmate-459) comparing sorafenib to nivolumab for the initial treatment of advanced HCC is ongoing.

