4.1 Inclusion Criteria

1. Subjects must have hepatocellular carcinoma (HCC) that is inoperable (where surgery is not indicated due to disease extent, co-morbidities, or other technical reasons)
2. Histologic confirmation of HCC is not required for screening but is required prior to initiation of study treatment. Subjects with hepatocholangiocarcinoma or cholangiocarcinoma are not eligible.
3. Tumor must be positive for retinoblastoma (RB) expression by immunohistochemistry
4. Age \geq 18 years and ability to understand and the willingness to sign a written informed consent document.
5. ECOG performance status of 0 or 1
6. Childs-Pugh score of ≤ 7
7. Life expectancy of at least 12 weeks
8. Must be able to swallow tablets
9. Must be willing to comply with protocol procedures (including completion of diaries and outcome measures)
10. Local or loco-regional therapy to the liver (i.e. surgery, radiation therapy, hepatic arterial embolization, chemoembolization, radiofrequency ablation, percutaneous ethanol injection, or cryoablation) must have been completed ≥ 4 weeks prior to enrollment
11. Must be willing to undergo a pretreatment and on-treatment biopsy and have a tumor site that is accessible for core needle biopsy
12. Measurable or evaluable disease as defined by RECIST v. 1.1
13. Women of childbearing potential must have a negative serum pregnancy test performed within 7 days of the first dose of abemaciclib (see Appendix A for definition of childbearing potential). Female subjects of childbearing potential must use an approved contraceptive method (detailed in Appendix A) for the duration of the study and an additional 3 weeks after the final dose of abemaciclib.
14. Subjects with hepatitis B must have an HBV viral load < 100 IU/mL by PCR during screening
15. Must have adequate organ and hematopoietic function as defined below:

Table 5: Baseline Laboratory Parameters

Laboratory Test	Required Value
Absolute neutrophil count (ANC)	$\geq 1.5 \times 10^9/L$
Platelet count	$\geq 75,000 \times 10^9/L$
Hemoglobin	$\geq 8.0 \times 10^9/L$

CONFIDENTIAL

This material is the property of the University of Pennsylvania.

Alanine aminotransferase (ALT)	$\leq 3 \times \text{ULN}$
Aspartate aminotransferase (AST)	$\leq 3 \times \text{ULN}$
Serum creatinine	$\leq 1.5 \times \text{ULN}$
OR creatinine clearance (CrCl)	OR $\text{CrCl} \geq 50 \text{mL/min}$ by Cockcroft-Gault Formula
Total bilirubin	$\leq 2.0 \times \text{ULN}$
Serum albumin	$\geq 2.8 \text{ g/dL}$

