5.7 Subject Compliance Monitoring

Subjects will be required to maintain a pill diary documenting adherence to twice daily oral administration of abemaciclib. Study medication bottles will be brought to study visits at the start of each 28-day cycle and study diaries will be reviewed at the start of each cycle.

6 Study Procedures

Table 6: Schedule of Study Procedures

All labs and study visits have a window of +/- 4 days. All imaging has a window of +/- 7 days

Study Phase	Screening	Cycle 1 (35 days)				Cycle 2+ (28 days)		End of Study Visit ²	Follow-up ³
Study Days	-28 to 0	1 8 15¹ 29¹				1 15¹			
Treatment									
Abemaciclib		X-----				X			
Nivolumab			X			X			
Tests and Procedures									
Informed Consent	X								
Review Inclusion/ Exclusion Criteria	X								
Demographics/Medical History	X								X ³
Physical Examination	X	X	X			X		X	
Vital Signs: BP, HR, RR	X	X	X			X		X	
Height	X								
Weight	X	X				X		X	
ECOG PS	X	X	X			X		X	
Concomitant Medications	X	X				X		X	
IP Compliance						X		X	
AE Assessment		X	X			X		X	
CBC with differential ⁴	X	X	X	X	X	X	X ⁴	X	
Serum Chemistries ⁵	X	X	X	X	X	X	X ⁵	X	
TSH	X					X		X	
PT/aPTT ⁶	X					X ⁶		X ⁶	
Serum Pregnancy Test ⁷	X	X				X		X	
AFP ⁸	X	X ⁸				X ⁸		X ⁸	
HIV Screening ⁹	X								
Hepatitis B/C Screening ¹⁰	X	X ¹⁰				X ¹⁰		X ¹⁰	
Disease Assessment (CT or MRI) ¹¹	X					X		X	
Research Correlates									
Blood sample (50cc) ¹²	X		X	X ¹²		X		X	

CONFIDENTIAL

This material is the property of the University of Pennsylvania.

Tumor biopsy ¹³	X		X					
----------------------------	---	--	---	--	--	--	--	--

¹ Lab visit only

² Should occur within 30 days of end of protocol therapy

³ Follow-up will be through review of the available medical record and/or phone calls every 6 months for up to 2 years

⁴ CBC with differential including hemoglobin, white blood count, absolute neutrophil count, and platelet count. CBC will be repeated on day 15 of cycle 2 but is required on day 15 of subsequent cycles only if hematologic toxicity \geq Grade 2 by CTCAE v 5.0

⁵ Serum chemistries including sodium (Na), potassium (K), chloride (Cl), bicarbonate (HCO3), blood urea nitrogen (BUN), creatinine (Cr), albumin, total bilirubin, AST, ALT, and alkaline phosphatase. Chemistries will be repeated on day 15 of cycle 2 but are required on day 15 of subsequent cycles only if hepatotoxicity \geq Grade 1 by CTCAE v 5.0 or other toxicity measured by the panel \geq Grade 2 by CTCAE v 5.0 are present on day 1 of that cycle.

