7.10.2 Definition of Evaluable

Evaluable for toxicity: All patients will be evaluable for toxicity from the time of their first treatment with abemaciclib.

Evaluable for efficacy endpoints, including overall response: Only those patients who have measurable disease present at baseline, have received at least one cycle of therapy (including at least 50% of scheduled abemaciclib doses and at least 1 dose of nivolumab), and have had their disease re-evaluated by appropriate imaging after at least 4 and no more than 12 weeks from cycle 1 day 1 will be considered evaluable for efficacy endpoints including overall response. These patients will have their response classified according to the definitions stated below.

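### Early failures are removed from ORR, PFS and OS and replaced, so the test against 18% can exceed its 10% error rate and survival is overstated

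*Combined protocol and SAP*

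**What the plan says.** Section 8.4.2 opens: "To be eligible for efficacy endpoints (PFS, ORR, DOR, OS), subjects must have completed at least one cycle of therapy". It also requires a CT or MRI "at least 4 weeks and no more than 12 weeks after their baseline imaging", and ends: "Subjects who do not meet criteria for the efficacy analysis will be replaced". Section 7.10.2 gives a parallel but different definition. Subjects must have measurable disease, must "have received at least one cycle of therapy (including at least 50% of scheduled abemaciclib doses and at least 1 dose of nivolumab", and must have "imaging after at least 4 and no more than 12 weeks from cycle 1 day 1".

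Sections 4.4 and 8.3 size the trial on 27 evaluable subjects, so the filtered set is the set that is tested. Section 8.4 specifies an exact binomial test of ORR at one-sided 10%, and 8.3 sets the null at 18%, pooled from published PD-1 studies. Sections 7.10.7 and 7.10.8 start PFS and OS at first treatment and include death as an endpoint. Only the safety analysis (8.4.3) uses everyone given a dose of abemaciclib.

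**The concern.** Entry to the efficacy set depends on what happens after treatment starts. A subject who dies in cycle 1, or deteriorates and stops both drugs without a scan in the window, is replaced by someone who lasted longer. The loss is limited: a subject who completes cycle 1 and progresses on a scan inside the window stays in, and stopping one drug does not by itself exclude anyone.

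The primary decision compares ORR with a fixed historical 18%. If the dropped subjects respond less often than the rest, the evaluable ORR exceeds the all-treated ORR with no added drug effect, and the combination could pass while being no better than nivolumab alone. Section 1.3.1 describes the nivolumab study by subjects treated ("A total of 262 subjects were treated in the two phases of the study") and mentions no evaluability filter, but it does not say which denominator its response rates use. A like-for-like comparison is therefore not shown.

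PFS and OS are descriptive. Their clocks start at first treatment while entry requires surviving to a scan, so their medians carry guaranteed time.

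**Working it through.** **Inputs.** N = 27, null 0.18, alternative 0.36, one-sided alpha 0.10 (8.3, 8.4). Cycle 1 lasts 35 days and later cycles 28 (Table 6). The first planned scan is cycle 3 day 1, and baseline imaging may be up to 21 days before cycle 1 day 1 (Table 6, footnote 11). Assumed, because the documents do not give them: the fraction dropped, d, and the response rate among those dropped, q.

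**The plan's own figure.** The smallest r with P(X ≥ r | 27, 0.18) ≤ 0.10 is 8. Alpha is 0.0977 (r = 7 gives 0.200) and power at 0.36 is 0.812. This reproduces the stated 81%.

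**Fragility at the cut-off.** With 8 responders:
- one treated non-responder replaced: P(X ≥ 8 | 28, 0.18) = 0.116, and the cut-off for 28 is 9
- three replaced: P(X ≥ 8 | 30, 0.18) = 0.158

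**Error of the 8/27 rule when the all-treated ORR is 18%.** Evaluable ORR = (0.18 − d·q)/(1 − d), and error = P(X ≥ 8 | 27, evaluable ORR). Example: d = 0.10 and q = 0 give 0.18/0.90 = 0.200, error 0.156.

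| Dropped, d | q = 0 | q = 0.09 | q = 0.18 |
|---|---|---|---|
| 5% | 0.123 | 0.110 | 0.098 |
| 10% | 0.156 | 0.125 | 0.098 |
| 20% | 0.248 | 0.164 | 0.098 |

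**A rough size for d from deaths alone.** Assume exponential survival, 30.44 days per month, and the protocol's own medians: 15.0 months (1.3.1), and 12 months as the upper limit of the statement in section 1. Then P(death by t) = 1 − 2^(−t/median).

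| Median | Dead by 35 days | Error (q = 0) | Dead by 63 days | Error (q = 0) |
|---|---|---|---|---|
| 15.0 months | 5.2% | 0.124 | 9.1% | 0.149 |
| 12 months | 6.4% | 0.132 | 11.3% | 0.165 |

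**Guaranteed time in OS.** Under exponential survival the median rises by the time that must be survived: 28/30.44 = 0.92 months (earliest scan in 7.10.2), 35/30.44 = 1.15 months (cycle 1 completed), and 63/30.44 = 2.07 months if entry depends on the cycle 3 day 1 scan. For PFS the loss is mainly early deaths, because radiographic progression is rarely detected before the first scan in any set.

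**Window conflict.** Cycle 3 day 1 falls 35 + 28 = 63 days after cycle 1 day 1. Table 6 adds "All imaging has a window of +/- 7 days", so the scan may be at 70 days. With baseline imaging 21 days before day 1, that is 91 days after baseline, beyond the 84-day (12-week) limit in 8.4.2. The same scan, 70 days from day 1, is inside the limit in 7.10.2.

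**Entry conflict.** Inclusion criterion 12 admits "Measurable or evaluable disease as defined by RECIST v. 1.1", whereas 7.10.2 counts only subjects with measurable disease.

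**The case against.** The size of the error inflation rests on two unknowns, the denominator behind 18% and the drop rate. If 18% came from a similarly filtered set, the inflation need not occur. That is right, and the 20% row has no support in the documents.

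The death-based figures lean towards a ceiling. The 7.10.2 window opens at week 4, and 6.2.4 and 6.2.6 call for imaging when treatment ends, so some subjects who die before cycle 3 would have a qualifying scan. Entry also requires ECOG 0 or 1, a Child-Pugh score of at most 7 and a 12-week life expectancy. These points reduce the size. Early stops for reasons other than death act the other way.

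Under 7.10.2 a subject who stops late in cycle 1 could remain evaluable; under 8.4.2 that subject could not. This is a reason to reconcile the two sections.

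An all-dosed set is not perfectly like-for-like either. Subjects lost during the seven-day abemaciclib run-in never receive nivolumab, a loss that a PD-1 monotherapy rate does not contain. This stands and should be reported.

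The window mismatch could exclude a responder and so lower ORR. It is a separate fault in the same definition.

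None of this defends removing early deaths from PFS and OS.

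**Conclusion.** The concern holds. Followed as written, the plan takes early deaths and early unscanned stops out of every efficacy result. The upward bias in OS and PFS follows from the text. Its size, roughly 1 to 2 months on the OS median, assumes exponential survival.

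Error above 10% in the primary test follows if dropped subjects respond less often and 18% is an all-treated rate. Under those conditions 5% to 10% dropped gives 0.110 to 0.156, depending on whether dropped subjects respond at 9% or not at all. With no link to response it stays at 0.098. The efficacy set is also not uniquely defined, because 7.10.2 and 8.4.2 differ on the scan anchor and on exposure, and 7.10.2 conflicts with criterion 12. This affects the primary decision and should be corrected before analysis.

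**What to change.** In 7.10.2 and 8.4.2:

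1. Make the primary set for ORR, PFS and OS all subjects given at least one dose of abemaciclib, the set already used for safety in 8.4.3. Count those without a usable post-baseline scan as non-responders, and deaths before the first scan as PFS events.
2. Keep the evaluable set as a sensitivity analysis, with counts and reasons for exclusion. Report separately those who never reached nivolumab.
3. If accrual still runs to 27 evaluable, test the all-treated count at the exact cut-off for the actual N, for example 9/30 (alpha 0.076) or 10/34 (alpha 0.072).
4. State the denominator behind the 18%.
5. Choose one anchor for the scan window and one exposure condition. Reconcile 7.10.2 with criterion 12: measurable disease is a baseline condition, so restricting ORR to dosed subjects who have it adds no bias of this kind. If non-measurable disease is kept, say how partial response is assigned.

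The change is to wording and uses data already collected. The cost is power:

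- **36% holds in all treated:** 9/30 and 10/34 have power 0.81 and 0.84.
- **36% holds only among the 27 evaluable:** the same rules have about 0.68 and 0.53. With 27 treated and 10% non-evaluable, power is 0.69 (8/27 at 0.9 × 0.36 = 0.324). Power of 0.81 needs 35 treated at 5% non-evaluable (cut-off 10) or 44 at 10% (cut-off 12).

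These figures hold N fixed. If N is random because accrual stops at 27 evaluable, power at 5% and 10% non-evaluable is about 0.78 and 0.80 on the first basis and 0.71 and 0.66 on the second, with error about 0.07.

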8.4.3 Safety Analysis

All subjects entered into the study and who are given at least one dose of abemaciclib will have detailed information collected on adverse events for the overall study safety analysis. All adverse events will be categorized by CTCAE v. 5.0, tabulated as ordinal, and summarized as binomial proportions.

8.4.4 Exploratory Endpoints

Analysis of Immune markers in tissue and blood will be a hypothesis-generating exploration of potential biomarkers. Logistic regression will be used to evaluate any association of response status with marker, and markers will be summarized by response status. Cox-proportional hazards regression models will be used to evaluate for any association with a marker and time to progression

9 Safety and Adverse Events

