4.4 Total Number of Subjects and Sites

Twenty-seven evaluable subjects will be enrolled. Subjects may be enrolled at the University of Pennsylvania or at the Penn Presbyterian Medical Center.

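### With about 5-10 responders expected, the marker-response logistic regression in Section 8.4.4 should name a penalised estimator: maximum likelihood overstates real effects and can fail to give a finite odds ratio for low-prevalence binary markers

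*Combined protocol and SAP*

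**What the plan says.** Section 8.4.4 (Exploratory Endpoints) sets the marker-response analysis in one sentence: "Logistic regression will be used to evaluate any association of response status with marker, and markers will be summarized by response status". It gives the status of the work as follows: "Analysis of Immune markers in tissue and blood will be a hypothesis-generating exploration of potential biomarkers". It does not state the estimator, the type of test or interval, how markers are coded, how many enter a model, or any rule for ranking or selecting them.

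The size of the data set comes from elsewhere. Section 4.4 says: "Twenty-seven evaluable subjects will be enrolled". Section 8.3 gives the response rates: "Doubling of this response rate, from 18% (H0) to at least 36% (H1) would be highly promising and worthy of additional study".

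The marker list is open. Section 7.11.1 adds to the named blood assays: "Depending on resource and sample availability, additional assays to further assess immune activation following treatment will be employed". Section 7.11.2 lists many tissue markers, including PD-L1 by immunohistochemistry, and says of the tissue itself: "Biopsies are mandatory but can be omitted if in the best interest of the subject".

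**The concern.** Logistic regression with no further qualification normally means maximum likelihood. That estimator needs a reasonable number of events, and here the events are responders. With very few of them, two things go wrong. Coefficients of markers that truly predict response are biased away from zero. And if a binary marker leaves an empty cell in its two-by-two table with response, no finite odds ratio exists; software then prints a very large number with a very large standard error, or a warning.

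At stake is the quality of the biomarker leads in the exploratory objective (Section 2.3). Inflated effect sizes could be carried into the planning of a later study. Separated markers would have to be handled by a method chosen after the data are seen.

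**Working it through.** **1. Inputs.** From the documents: n = 27 evaluable (Section 4.4); response rates of 18% and 36%, one-sided alpha 0.10, power 81% (Section 8.3); 20% of subjects with PD-L1 above 1% in the nivolumab HCC study described in Section 1.3.1. Assumed, because the documents are silent: one marker per model; a marker that is either continuous (normal, odds ratio per SD) or binary; true odds ratios of 1, 2 or 3.

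**2. The plan's own figure.** The documents give no figure for the marker regression. The power statement reproduces: declaring success at 8 or more responders of 27, the exact binomial test has alpha = P(X ≥ 8 | 0.18) = 0.0977 and power = P(X ≥ 8 | 0.36) = 0.812, that is, 81%.

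**3. Number of events.** 27 × 0.18 = 4.9 and 27 × 0.36 = 9.7, so about 5 to 10 responders. At 18% the chance of fewer than 5 is 0.45.

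**4. Empty cells for a binary marker with no association.** 20% of 27 is 5.4, so 5 positives is a fair case for PD-L1 if it is dichotomised at 1%. With R responders and 5 positives, where R is at least 5, an empty cell arises when no positive is a responder or when every positive is one:

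P = [C(27 − R, 5) + C(R, 5)] / C(27, 5), with C(27, 5) = 80,730.

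- R = 5: (26,334 + 1) / 80,730 = 0.326
- R = 8: (11,628 + 56) / 80,730 = 0.145
- R = 10: (6,188 + 252) / 80,730 = 0.080

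Five responders with 8 positives gives 0.145 as well, by symmetry.

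If both counts vary at random (20% prevalence, n = 27), the chance of no finite odds ratio is 39% at an 18% response rate and 16% at 36%. These figures include data sets in which the marker or the response does not vary. With an assumed 20 tissue samples they become 52% and 28%.

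**5. Bias for a continuous marker.** Simulation with 20,000 data sets per setting, n = 27 and 5, 7 or 10 responders, gave these mean log odds ratios:

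| True odds ratio | True log odds ratio | Maximum likelihood | Firth |
|---|---|---|---|
| 2 | 0.69 | 0.83-0.87 | 0.70-0.71 |
| 3 | 1.10 | 1.35-1.46 | 1.11-1.13 |

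The overstatement runs from 0.83/0.69 = 1.20 to 1.46/1.10 = 1.33, so about 20-33%. The means have a long upper tail, so the second decimal depends somewhat on how nearly separated data sets are handled. Separation occurred in at most 0.5% of data sets. With a true odds ratio of 1, the mean log odds ratio was about 0.

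A separate simulation with a true log odds ratio of 0.80 gave means of 1.00 by maximum likelihood and 0.83 by Firth. Root mean squared error fell from 0.79 to 0.59.

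**6. What a screen would do with null markers.** Over the same settings, at nominal two-sided 0.05, the Wald test rejected 0.3-4.5% of the time and the likelihood-ratio test 5.0-8.6%. In separated data sets the Wald test was never significant. For null binary markers at 20% prevalence, an estimated odds ratio above 3 or below 1/3 occurred in 35-48% of data sets by maximum likelihood and 24-29% by Firth.

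**The case against.** A reader might infer that the planned screen favours spurious markers. The documents do not support that.

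- Section 8.4.4 states no ranking, cut-off or selection rule, and the direction of the error depends on that rule. Ranking by raw odds ratio would promote sparse null markers. A Wald p-value screen would drop separated markers, including any that discriminate well. A likelihood-ratio screen is at nominal or mildly above.
- The typical empty-cell table is visibly uninformative. For 0 of 5 responders positive against 5 of 22 non-responders, Fisher's two-sided p is 44,155/80,730 = 0.55. For the 8-positive case (0 of 5 against 8 of 22) it is 0.28. The planned summary of markers by response status would show the empty cell directly.
- Inflating a real effect does not create a false marker, and null continuous markers show no average inflation.

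Other parts of the opposing case also stand. Many of the listed assays are naturally quantitative and rarely separate. Dichotomising PD-L1 is an assumption. Loss of tissue is less likely at baseline, since Section 7.11.2 requires tissue confirmation of histology and RB status before therapy. Firth or exact estimation would also fit the text, so this is an unspecified detail rather than a stated wrong choice. The number of markers is a larger source of false leads: 20 independent null markers, each tested at an assumed 0.05, give 1 − 0.95^20 = 64% chance of at least one false positive, and a penalty does not change that.

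None of this removes the estimation problem. Exploratory status excuses low power and the absence of alpha control, but it is no reason to leave in place an estimator whose bias and non-existence at the planned size can be foreseen.

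**Conclusion.** The concern holds as a minor point about the estimator. If logistic regression is read as maximum likelihood, then at 5 to 10 responders real continuous-marker effects are overstated by about 20-33% on the log odds scale. A binary marker positive in 5 of 27 subjects has no finite odds ratio in 33% (5 responders) to 8% (10 responders) of data sets under no association. The first result rests on a single normally distributed marker with a true odds ratio of 2 or 3. The second rests on dichotomisation at about 20% prevalence. For single continuous markers, failure to obtain an estimate is not a practical issue. The claim that the screen selects spurious markers should not be made. No primary or secondary endpoint, sample size or trial decision is affected.

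**What to change.** In Section 8.4.4, specify that each marker's association with response will be estimated by Firth-penalised logistic regression, one marker per model, with penalised profile-likelihood confidence intervals. In the simulations this gave a finite estimate in every data set and was close to unbiased for continuous markers.

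The cost is one sentence and standard software. The downside is that estimates are shrunk slightly toward zero. The change does not address multiplicity. Stating how markers are coded and how many were tested and reported would help a reader judge that separately.
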